9.3	Clinical Laboratory Data	18
9.4	Vital Sign Data	18
9.5	Physical Examination Data	18
9.6	Electrocardiogram Data.....	19
9.7	Other Safety Data	19
10	Pharmacokinetic Analyses.....	19
10.1	Endpoints.....	19
10.2	Analysis Set.....	19
10.3	Handling of Data	19
10.4	Statistical Analyses	19
11	Pharmacodynamic Analyses.....	20
12	Pharmacogenomic Analyses	20
13	Interim Analysis	21
14	Changes in the Planned Analyses	21
15	References	21

List of Appendices

Appendix 1	List of Summary Tables.....	22
Appendix 2	List of Subject Data Listings	29
Appendix 3	Molecular Weight and Lower Limit of Quantification for Plasma Drug Concentrations	31

List of Abbreviations and Definition of Terms

Abbreviation	Definition
AE	Adverse event
ANCOVA	Analysis of covariance
AVP	Arginine vasopressin
BNP	Brain natriuretic peptide
CHF	Congestive heart failure
CRF	Case report form
ICH	International Conference on Harmonisation
IMP	Investigational medicinal product
MedDRA	Medical Dictionary for Regulatory Activities
NYHA	New York Heart Association
PT	Preferred Term
SOC	System Organ Class
TEAE	Treatment-emergent adverse event
ULN	Upper limit of normal

1 Introduction

This statistical analysis plan documents the details of the statistical analysis methodology to be applied in the protocol of Trial 263-102-00003.

2 Trial Objectives

Primary: To confirm the non-inferiority of OPC-61815 16-mg injection to tolvaptan 15-mg tablet using as the primary endpoint the change in body weight following 5-day intravenous administration of OPC-61815 16-mg injection or 5-day oral administration of tolvaptan 15-mg tablet to congestive heart failure (CHF) patients with volume overload despite having received diuretics other than vasopressin antagonists.

Secondary: To evaluate other efficacy endpoints and the safety, pharmacodynamics, and pharmacokinetics of OPC-61815 16-mg injection in comparison with tolvaptan 15-mg tablet.

3 Trial Design

3.1 Type/Design of Trial

This trial will be conducted in 288 CHF patients with volume overload despite having received diuretics other than vasopressin antagonists. The subjects will be randomly assigned to either of the OPC-61815 16-mg injection group or the tolvaptan 15-mg tablet group (144 patients per group) to confirm the non-inferiority of OPC-61815 16-mg injection to tolvaptan 15-mg tablet in an active control, randomized, double-blind, parallel group, multicenter design.

The 3 days before start of investigational medicinal product (IMP) administration comprise the run-in period, during which the use of diuretics, change in body weight, and congestive symptoms are assessed. After the run-in period, only subjects who meet the inclusion criteria (run-in period) will enter into the treatment period during which the IMP will be administered once daily for 5 days. The doses and dosage regimens of diuretics that have been used since before start of the run-in period must be maintained until the end of the treatment period. The completion assessment will be performed on Day 6 (day after final IMP administration), and the follow-up assessment will be performed at some time between Day 12 and Day 15.

This trial will employ a double-dummy method to maintain blindness. Subjects will receive either of a combination of OPC-61815 16-mg injection and placebo tablet or a combination of placebo injection and tolvaptan 15-mg tablet. Subjects will be

hospitalized from the day before start of the run-in period (Day -4) to the end of the treatment period (Day 6).

3.2 Trial Treatments

The investigator or subinvestigator will instruct subjects to ingest one tolvaptan 15-mg tablet or one placebo tablet with water once daily. Immediately after the intake of the tablet, the investigator or subinvestigator will administer OPC-61815 16-mg injection or placebo injection as a 1-hour (55 to 65 minutes allowable) infusion once daily for 5 days according to the IMP administration procedures specified separately. Subjects will be asked to take breakfast and then urinate to start the measurement of daily urine volume immediately before receiving the administration of IMPs on each of the 5 days. The start time of administration on Day 2 and onward should be within 20 minutes before or after the start time on Day 1, if possible. The investigator or subinvestigator will confirm that administration of the IMPs has been completed, and record the following information in the source document and the eCRF (electronic case report form): the date and time of the start and end of the administration (and the suspension period, if the administration is suspended), and whether or not the entire dose has been administered; and, the date and time of administration for the tablet. The IMPs will also be administered to subjects who do not take breakfast.

3.3 Trial Population

The necessary sample size is 288 subjects (144/group). Subjects are required to be Japanese male and female CHF patients age of 20 to 85 years, inclusive, with volume overload (ie, lower limb edema, pulmonary congestion, and/or jugular venous distension) despite having received diuretics other than vasopressin antagonists, who will be able to be hospitalized from the day before start of the run-in period through the end of the treatment period and take oral tablets.

3.4 Handling of Time Points

Case report form (CRF) Visit values at each time point (run-in period, treatment period, and follow-up) will be used in summaries (but values at the time of discontinuation will not be used in summaries). Unscheduled Visit values will not be used.

Baseline and final administration time point for each variable are defined as follows.

Variable	Baseline ^a	Final Administration Time Point
Body weight	Before IMP administration on Day 1	Day after final IMP administration
Congestive symptoms (lower limb edema, jugular venous distension, hepatomegaly, pulmonary rales, third cardiac sound)	Run-in period (final measurement)	Day after final IMP administration
Pulmonary congestion, cardiothoracic ratio	Run-in period	Day after final IMP administration
NYHA classification	Run-in period	Day after final IMP administration
Clinical laboratory value	Before IMP administration on Day 1	Day after final IMP administration
Vital signs	Before IMP administration on Day 1	Day after final IMP administration
12-lead ECG	Before IMP administration on Day 1	Day after final IMP administration
Serum sodium concentration, serum potassium concentration, serum osmolality, biomarker	Before IMP administration on Day 1	-
Daily urine volume, daily fluid intake, daily fluid balance, daily urine sodium excretion, daily urine potassium excretion, urine osmolality	Within 24 hours before start of IMP administration on Day 1	-

^aWhen multiple data are collected during the run-in period, the data closest to Day 1 will be used as baseline.

4 Sample Size

The number of subjects required to confirm the non-inferiority of OPC-61815 16-mg injection to tolvaptan 15-mg tablet for the primary endpoint of change in body weight from baseline (before IMP administration on Day 1) at the time of final IMP administration (day after final IMP administration) was determined.

In the clinical development of tolvaptan for the treatment of cardiac edema, there were 2 placebo-comparison trials conducted for tolvaptan 15-mg tablet: a phase 2 trial (156-03-001) and a phase 3 trial (156-06-002). Regarding the change in body weight (kg) on the morning after Day 5 of treatment (LOCF) in those 2 trials, from an analysis of covariance (ANCOVA) model analysis performed using body weight (kg) at baseline as a covariate, the least-square mean of the difference (treatment difference) between the tolvaptan 15-mg tablet group and the placebo group was respectively -0.99 (95% CI: -1.57 to -0.42) and -0.96 (95% CI: -1.37 to -0.55). Referring to the upper limit of those

CIs, the reliably expected (at 95% probability) minimum difference in body weight decrease (maximum difference in body weight) between the tolvaptan 15-mg tablet group and the placebo group was considered to be in the range of 0.42 to 0.55. The non-inferiority margin for the present trial was therefore set at 0.48, which corresponds to half of the treatment difference of 0.96 between the tolvaptan 15-mg tablet group and the placebo group in the tolvaptan phase 3 trial.

Setting the non-inferiority margin at 0.48, the detection power at 90%, and the significance level at 5%, and using the value for up until the morning after Day 5 of treatment in the tolvaptan 15-mg tablet in the tolvaptan phase 3 trial to set the mean \pm SD change in body weight from baseline at time of final administration at -1.30 ± 1.25 for both the tolvaptan 15-mg tablet group and the OPC-61815 16-mg injection group, the number of subjects required for this trial was determined to be 288 (144 subjects per group).

5 Statistical Analysis Datasets

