3.7.1.2 Run-in Period (Day -3, Day -2, and Day -1)

The investigator or subinvestigator will conduct the following examinations and tests to assess the eligibility for a shift to the treatment period. Diuretics that have been used since start of the run-in period (Day -3) will be continued to be used with the same doses and dosage regimens until the completion (withdrawal) assessment, regardless of the previous use or method of use before run-in period.

Subjects must be hospitalized from the day before start of the run-in period through the completion (withdrawal) assessment.

1) Each day during the run-in period

a) Before breakfast

- Body weight
- Vital signs (blood pressure, pulse rate, and body temperature)

b) After breakfast

Subject are required to urinate completely immediately after breakfast, and then urine collection and fluid intake measurement will start to assess the following items.

- Daily urine volume

- Daily fluid intake

- Daily fluid balance (difference between daily fluid intake and daily urine volume)

- Daily urine sodium excretion and daily urine potassium excretion (calculated from urine sodium concentration, urine potassium concentration, and daily urine volume)

- Urine osmolality

c) At a feasible time

- Congestive symptoms (lower limb edema, jugular venous distension, hepatomegaly, pulmonary rales, and cardiac third sound)

- Adverse events, physical examination

- Concomitant medications and therapies

2) Any single day during the run-in period

The following examinations will be conducted once at a feasible time.

- Chest x-ray (cardiothoracic ratio and pulmonary congestion)
- NYHA classification

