3.7.1.7 Treatment Period (Days 4 and 5)

1) Before breakfast

- Serum sodium concentration and sodium potassium concentration
- Body weight
- Vital signs (blood pressure, pulse rate, and body temperature)

2) After breakfast

Subject are required to urinate completely immediately after breakfast, and urine collection and fluid intake measurement will start to assess the following items from the point at which urination immediately before IMP administration has been completed.

- Daily urine volume, daily fluid intake, and daily fluid balance
- Daily urine sodium excretion and daily urine potassium excretion
- Urine osmolality

3) IMP administration

4) At a feasible time on each day

- Congestive symptoms (lower limb edema, jugular venous distension, hepatomegaly, pulmonary rales, and cardiac third sound)
- Adverse events, physical examination
- Concomitant medications and therapies
- Confirmation of IMP compliance

3.7.1.8 Treatment Period (Completion Assessment on Day 6 or Withdrawal Assessment on Day After the Final IMP Administration)

The investigator or subinvestigator will conduct the completion assessment on Day 6 as described below. If IMP treatment is discontinued before Day 6 for any reason, the same assessment as the completion assessment for Day 6 will be conducted at a feasible time as the withdrawal assessment on day after final IMP administration, whenever possible, and then follow-up will be made 7 to 10 days after the final IMP administration. During the withdrawal assessment, plasma drug concentrations will be measured (at a feasible time), whenever possible. Information on trial completion or trial withdrawal will be entered into the IWRS.

1) Before breakfast

- Serum sodium concentration, serum potassium concentration, serum osmolality, and biomarkers
- Body weight
- Clinical laboratory tests and vital signs (blood pressure, pulse rate, and body temperature)

2) At a feasible time

- Blood sampling for measurements of plasma drug concentrations (only at the withdrawal assessment)

- Congestive symptoms (lower limb edema, jugular venous distension, hepatomegaly, pulmonary rales, and cardiac third sound)
- Chest x-ray (cardiothoracic ratio and pulmonary congestion)
- NYHA classification
- Adverse events, physical examination
- 12-Lead ECG
- Concomitant medications and therapies

3.7.1.9 Follow-up After Completion of the Treatment Period (Day 12 to Day 15, 7 to 10 Days After the Final IMP Administration)

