5.5 Handling of Missing Data

If the data at the time of final assessment (on the day after final IMP administration) is missing, the last available data obtained by the day after final IMP administration will be used (efficacy and safety).

6 Primary and Secondary Outcome Variables:

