8.1 Primary Efficacy Endpoint

The primary endpoint is the change in body weight from baseline (before IMP administration on Day 1) at time of final IMP administration (day after final IMP administration), and the non-inferiority of OPC-61815 16-mg injection to tolvaptan 15-mg tablet in the change from baseline in body weight will be confirmed with a noninferiority margin of 0.48.

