8.3.4 NYHA Classification

A shift table for the NYHA classification from baseline at the time of final IMP administration and each timepoint by treatment group will be prepared.

For Class II and higher subjects, the proportion of those who have improved from baseline by 1 or more NYHA class at the time of final IMP administration will be calculated for each treatment group to determine the difference between the OPC-61815 16 mg injection group and the tolvaptan 15 mg tablet group and its two-sided 95% CI (exact).

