9.4 Vital Sign Data

For vital signs, measured values and changes from baseline at each time point and at the time of final IMP administration will be summarized using descriptive statistics.

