Appendix 1**List of Summary Tables**

CT-1 Subject Disposition (Screened Subjects)

CT-2.1 Reasons for Discontinuation (Randomized Subjects)

CT-2.2 Protocol Deviations (Randomized Subjects)

CT-3.1.1 Demographic and Baseline Characteristics (Full Analysis Set)

CT-3.1.2 Demographic and Baseline Characteristics (Safety Analysis Set)

CT-3.2.1 Underlying Disease Leading to Heart Failure (Full Analysis Set)

CT-3.2.2 Underlying Disease Leading to Heart Failure (Safety Analysis Set)

CT-3.2.3 Medical History (Full Analysis Set)

CT-3.2.4 Medical History (Safety Analysis Set)

CT-3.3.1 Concomitant Medications Used on the First Day of Trial Drug Administration (Full Analysis Set)

CT-3.3.2 Concomitant Medications Used on the First Day of Trial Drug Administration (Safety Analysis Set)

CT-3.4.1 Baseline Disease Evaluation (Full Analysis Set)

CT-3.4.2 Baseline Disease Evaluation (Safety Analysis Set)

CT-5.1 Analysis of Covariance for Change from Baseline in Body Weight at the time of Day After Final IMP Administration (Full Analysis Set)

CT-5.2 Descriptive Statistics for Change from Baseline in Body Weight (Full Analysis Set)

CT-5.3 Descriptive Statistics for Change Rate from Baseline in Body Weight (Full Analysis Set)

CT-5.4 Treatment Difference for Change From Baseline in Body Weight at the time of Day After Final IMP Administration (Full Analysis Set)

CT-5.5 Subgroup Analysis for Change from Baseline in Body Weight at the time of Day After Final IMP Administration (Full Analysis Set)

CT-6.1.1 Improvement Rate for Lower Limb Edema and Pulmonary Congestion at the time of Day After Final IMP Administration (Full Analysis Set)

CT-6.1.2 Improvement Rate for Lower Limb Edema (Full Analysis Set)

- CT-6.2 Disappearance Rate for Lower Limb Edema and Pulmonary Congestion at the time of Day After Final IMP Administration (Full Analysis Set)
- CT-6.3 Shift Table for Lower Limb Edema (Full Analysis Set)
- CT-6.4 Shift Table for Pulmonary Congestion (Full Analysis Set)
- CT-6.5.1 Analysis of Covariance for Change from Baseline in Jugular Venous Distension at the time of Day After Final IMP Administration (Full Analysis Set)
- CT-6.5.2 Analysis of Covariance for Change from Baseline in Jugular Venous Distension at the time of Day After Final IMP Administration (Subjects With Baseline Value in Full Analysis Set)
- CT-6.6.1 Analysis of Covariance for Change from Baseline in Hepatomegaly at the time of Day After Final IMP Administration (Full Analysis Set)

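### Does SAP 3.4 remove early stoppers' withdrawal values from the final time point, and so from the primary analysis?

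*SAP*

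**What the plan says.** SAP 3.4 opens by saying that visit values recorded on the case report form, for run-in, treatment and follow-up, are used in summaries, and adds in a parenthesis "but values at the time of discontinuation will not be used in summaries". It then defines, variable by variable, a baseline and a final administration time point. For body weight, congestive symptoms, chest x-ray findings and NYHA class, the latter is the day after the final dose.

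SAP 8.1 sets the primary endpoint as the change in weight "at time of final IMP administration (day after final IMP administration"). If that assessment is missing, SAP 5.5 says "the last available data obtained by the day after final IMP administration will be used (efficacy and safety"). Protocol 7.3 has the same rule.

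For a subject who stops before Day 6, Protocol 3.7.1.8 says that the Day 6 assessments "will be conducted at a feasible time as the withdrawal assessment on day after final IMP administration", whenever possible.

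NYHA class and chest x-ray have only one run-in assessment (Protocol 3.7.1.2: "The following examinations will be conducted once at a feasible time"). They are next assessed at Day 6 or withdrawal. SAP 8.3.4 reports "the proportion of those who have improved from baseline by 1 or more NYHA class", and SAP 8.3.1 gives similar rates for pulmonary congestion.

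**The concern.** For an early stopper, the value on the day after the last dose is the withdrawal value. SAP 3.4 appears to require it in the table and to bar it in the parenthesis. Two features encourage the literal reading. Appendix 1 places CT-5.1, "Analysis of Covariance for Change from Baseline in Body Weight at the time of Day After Final IMP Administration", under a heading about summary tables. The safety sections also use the language of summaries for the final time point; SAP 9.4, for example, covers "measured values and changes from baseline at each time point and at the time of final IMP administration".

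If the withdrawal value were dropped and SAP 5.5 then applied, there would be two effects:

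- **Weight.** It is measured before breakfast and dosing follows breakfast, so the carried value would precede the last dose and miss its effect. After a single dose, only the baseline weight might remain.
- **NYHA class and chest x-ray.** The run-in value would be carried forward and the subject scored as unchanged.

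The literal reading shrinks weight loss in whichever arm has more early stopping. If that is the tolvaptan arm, the shift favours OPC-61815 in a non-inferiority comparison. SAP 8.1.2 plans no sensitivity analysis that would show it.

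**Working it through.** **What the literal reading needs.** All three of these steps must hold.

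1. *The word for summaries must include the primary ANCOVA.* In SAP 8.1.1 and 8.3.2 the ANCOVA is described as an analysis, and summarizing refers to descriptive statistics by time point. The Appendix 1 heading does not define the term: the same list holds subject listings (CT-9.7 to CT-9.9) and figures (CF-1 to CF-7). SAP 9.3 and 9.4 do use the term for the final time point, but they are safety sections and name that time point separately from the visits.
2. *A general parenthesis must override a specific definition.* The parenthesis qualifies a sentence about visit values. The table below it defines the final administration time point, and for early stoppers Protocol 3.1 (note to the design figure) and 3.7.1.8 schedule exactly that assessment. The literal reading would largely empty the definition for every non-completer.
3. *A collected value must count as missing.* SAP 5.5 applies only when the final assessment is missing. Its window runs up to and including the day after the last dose, so a withdrawal weight taken that day is itself the last available value.

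Protocol 7.3 and 7.4.1 contain no exclusion of discontinuation values, and SAP 14 declares no changes to the planned analyses. The literal reading would be an undeclared change to the primary endpoint.

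**The plan's own figure.** Inputs from SAP 4: margin 0.48, SD 1.25, true difference 0, power 90%. The two-sided 95% interval gives 0.025 one-sided.

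- Normal approximation: n = 2 × 1.25² × (1.960 + 1.282)² / 0.48² = 142.5, so 143 per group.
- With the t distribution, power is 89.9% at 143 and 90.1% at 144. The stated 144 per group (288) is reproduced.

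**Size if the literal reading were used.** The documents give no dropout rate for this trial, so the stopping rates are assumed.

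- Loss per affected stopper, linear course: 1.30 / 5 = 0.26 kg.
- Shift in the treatment difference = excess of early stoppers in one arm × 0.26.
- SE = 1.25 × √(2/144) = 0.1473, with 285 degrees of freedom.
- One-sided error is the chance that the upper limit is at or below 0.48 when the true difference is 0.48. With no shift it is 2.5%.

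| Excess of stoppers | Shift (kg) | Share of 0.48 | Error, excess on tolvaptan | Error, excess on OPC-61815 |
|---|---|---|---|---|
| 2 points | 0.0052 | 1.1% | 2.7% | 2.3% |
| 5 points | 0.013 | 2.7% | 3.1% | 2.0% |
| 10 points | 0.026 | 5.4% | 3.7% | 1.6% |

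With equal stopping the difference hardly moves. The shift scales with the assumed loss: at 0.52 kg per stopper, twice the linear figure, a 5 point excess gives 0.52 × 0.05 = 0.026 kg.

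The table also assumes that no stopper has a scheduled weight on the morning after the last dose. Weight is scheduled before breakfast on every treatment day, so a subject stopped later that morning already has one. The share affected is unknown, but it is below the whole excess if any such weights exist.

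**NYHA and pulmonary congestion.** Fall in an arm's improvement rate = share stopping × improvement rate among stoppers. Assuming 2% to 10% stopping and 30% to 70% improvement, this runs from 0.02 × 0.30 = 0.6 points to 0.10 × 0.70 = 7 points. These are secondary endpoints, and SAP 8.2 sets no key secondary endpoint.

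**The case for a change.** The best argument for acting is that this is the confirmatory endpoint of a non-inferiority trial, that nothing in the SAP states the scope of the parenthesis, and that a sentence would settle it at no cost. Unequal stopping is also not fanciful. In the phase 2 trial (Protocol 1.2.2), 3 of 12 tolvaptan subjects stopped for adverse events, against 2 of 48 on OPC-61815. Taken at face value, (3/12 − 2/48) × 0.26 = 0.054 kg, or 11% of the margin, with a one-sided error of 5.6%.

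The scope is indeed unstated, and that much stands. The phase 2 figure carries little weight: the exact 95% interval for 3/12 runs from about 5% to 57%, and the comparator pools 2 to 16 mg when this trial uses only 16 mg. Even then, the shift arises only if the less natural reading is adopted and no morning weight is available.

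A second point also stands in part. However SAP 3.4 is read, SAP 5.5 does not say whether a run-in NYHA class or x-ray may be carried forward when no withdrawal assessment was done. Carrying it forward scores the subject as not improved, which is a common convention. Requiring a post-dose value would leave the subject missing instead, and SAP 8.3.1 and 8.3.4 do not say how a missing endpoint enters the denominator. Neither choice is clearly better.

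**Conclusion.** No change to the plan follows. The parenthesis in SAP 3.4 is loosely worded, but with the table below it, Protocol 7.3 and 7.4.1, and SAP 14, its sensible meaning is that withdrawal values are kept out of the by-visit tables and used as the final value for early stoppers. An analyst would fill the gap that way, and the primary result would then be the one the protocol defines.

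The size of 0.005 to 0.026 kg (1% to 5% of the margin) applies only if the literal reading is adopted, early stopping differs by 2 to 10 points between arms, each affected stopper loses 0.26 kg, and no scheduled morning weight is available. The error of 3.7% further requires the 10 point excess to be on tolvaptan and the true difference to lie exactly at 0.48. The silence of SAP 5.5 on run-in NYHA and x-ray values is a matter of convention for secondary endpoints and does not touch the non-inferiority conclusion.
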